3 STUDY OBJECTIVE(S) AND DESIGN

3.1 Study Objective(s)

This is an extension study conducted in RA patients who have completed the Phase IIb Study of ASP015K [015K-CL-RAJ1 (hereinafter referred to as study RAJ1)], Phase III Study of ASP015K [015K-CL-RAJ3 (RAJ3)], or Phase III Study of ASP015K [015K-CL-RAJ4 (RAJ4)] to investigate the safety and efficacy of long-term administration of ASP015K.

Another objective of this study is to devise rescue measures for providing the active drug to patients who participated in the Phase IIb Study or Phase III Study of ASP015K, as described in the "Guidelines on methodology for clinical assessment of antirheumatic drugs" (PFSB/ELD Notification No. 0217001, dated 17 February, 2006).

3.2 Study Design

This study is an extension study conducted as an open-label, multicenter study in RA patients who have completed studies RAJ1, RAJ3, or RAJ4.

Patients who meet all the inclusion criteria and do not fall under any of the exclusion criteria will receive oral ASP015K 100 mg QD after breakfast as the starting dose. Subjects who have no safety problems but show lack of efficacy may later increase the dose to 150 mg/day. After the increase, the dosage may be reduced from 100 mg/day or 150 mg/day to 50 mg/day at the discretion of the investigator or sub-investigator. The starting dose for subjects who transferred from study RAJ1 is 50 mg/day. For subjects who transferred from study RAJ1 and are continuing to receive 50 mg/day, treatment extension using a dose of 50 mg/day should be allowed when the investigator or sub-investigator considers a dose increase to be inappropriate in terms of safety and treatment extension with a dose of 50 mg/day to provide greater therapeutic benefit for the treatment of RA.

Because this study will end at the point in time when ASP015K is approved, the duration of treatment with the study drug will differ depending on the subject. To prevent purposeless continuation of dosing without effect, the investigator or sub-investigator will assess each subject for efficacy and safety at each visit, confirm the appropriateness of continued administration for each individual, and decide whether or not to continue dosing.

3.3 Randomization

Not applicable.

4 SAMPLE SIZE

Approximately 800 treated patients

[Rationale for the sample size]

The sample size estimation is based on the number of subjects who have completed the preceding study of ASP015K (Study 015K-CL-RAJ1) and participate in this extension study (201 subjects), the planned number of subjects in Study 015K-CL-RAJ3 excluding those in the reference group (300 subjects), and the planned number of subjects in Study 015K-CL-RAJ4 (510 subjects).

5 ANALYSIS SETS

In accordance with International Conference on Harmonization (ICH) recommendations in guidelines E3 and E9, the following analysis sets will be used for the analyses.

5.1 Full Analysis Set (FAS)

The FAS is defined as all subjects who receive at least one dose of study drug and have measurements for any of the efficacy endpoints.

5.2 Safety Analysis Set (SAF)

The SAF is defined as all subjects who received at least one dose of the study drug.

5.3 Pharmacodynamic Analysis Set (PDAS)

The PDAS is defined as all subjects who receive at least one dose of the study drug and from whom a pharmacodynamics sample is collected at one or more points of time.

6 ANALYSIS VARIABLES

6.1 Efficacy Endpoints

6.1.1 Categorical Variables

- Percentage of subjects achieving ACR 20/50/70-CRP response at each analysis visit
- Percentage of subjects achieving ACR 20/50/70-ESR response at each analysis visit

Definition ACR20 response rate:

It is defined as percentage of subjects achieving ACR 20 response at each study visit, based on C-reactive protein (CRP). ACR20 is a binary variable, with levels responder and non-responder.

Responder:

A subject will be defined as an ACR20-CRP responder at any time point (e.g. Week 12) if the subject meets ALL the following American College of Rheumatology (ACR) response criteria:

• At least 20% reduction from baseline at the time point (e.g. Week 12) in the number of 68 tender joint count (TJC-68)

AND

• At least 20% reduction from baseline at the time point (e.g. Week 12) in the number of 66 swollen joint count (SJC-66)

AND

- At least 20% reduction from baseline at the time point (e.g. Week 12) in ANY 3 or more of the 5 following ACR components
 - O Subject's global assessment of arthritis pain (SGAP) (assessed using a 100 mm VAS ; score of 0 indicates no pain, and score of 100 indicates very severe pain)
 - Subject's global assessment of arthritis (SGA) (assessed using a 100 mm VAS; score
 of 0 indicates no disease activity, and score of 100 mm indicates very severe disease
 activity)
 - Physician's global assessment of arthritis (PGA) (assessed using a 100 mm VAS;
 score of 0 indicates no disease activity, and score of 100 mm indicates very severe disease activity)
 - Health Assessment Questionnaire Disease Index (HAQ-DI; score ranges from 0 to 3 with higher scores indicating greater disability)
 - CRP (Higher values indicate greater inflammation)

Values at the baseline in the preceding studies (RAJ1, RAJ3, and RAJ4) will be used as the baseline values. A negative percent change indicates a reduction from baseline (i.e., a favorable outcome). If the baseline value is 0 in some of ACR components, then that

component is not included in ACR calculation at any visit and ACR response is calculated based on remaining non-missing components.

Non-responder: A subject will be defined as an ACR20-CRP non-responder at the time point (e.g. Week 12), if the subject does not meet the ACR20-CRP responder criteria.

Note: ACR 20/50/70-ESR response is similar to the above by replacing CRP with ESR.

- Percentage of subjects achieving DAS28-CRP score <2.6 at each analysis visit
- Percentage of subjects achieving DAS28-ESR score <2.6 at each analysis visit
- Percentage of subjects achieving DAS28-CRP score <=3.2 at each analysis visit
- Percentage of subjects achieving DAS28-ESR score <=3.2 at each analysis visit

Calculation DAS28-CRP/ESR response:

DAS28-CRP/ESR response is consist of following parameters, and calculated according to below description.

- o TJC (28 joints)
- o SJC (28 joints)
- CRP or ESR
- SGA

```
[When CRP is used] DAS28 = 0.56\sqrt{(TJC)} + 0.28\sqrt{(SJC)} + 0.36 \ln{(CRP + 1)} + 0.014 \times SGA + 0.96 [When ESR is used] DAS28 = 0.56\sqrt{(TJC)} + 0.28\sqrt{(SJC)} + 0.70 \ln{ESR} + 0.014 \times SGA
```

Note: CRP values measured in mg/dL will be converted to mg/L for analysis purposes as: value in mg/L = value in mg/dL \times 10; SGA is measured on 100 mm VAS. If any component is a missing value, then DAS28-CRP/ESR will be a missing value. If ESR is 0 then DAS28-ESR is missing.

- Percentage of subjects in DAS28-CRP EULAR response criterion of "Good Response" at each analysis visit
- Percentage of subjects in DAS28-ESR EULAR response criterion of "Good Response" at each analysis visit
- Percentage of subjects in DAS28-CRP EULAR response criterion of "Good Response" or "Moderate Response" at each analysis visit
- Percentage of subjects in DAS28-ESR EULAR response criterion of "Good Response" or "Moderate Response" at each analysis visit

Definition EULAR response:

DAS28 after treatment	DAS28 improvement (DAS28 before treatment - DAS28 after treatment)										
DAS28 after treatment	> 1.2	> 0.6 and $<= 1.2$	<= 0.6								
<= 3.2	Good response	Moderate response	No response								
> 3.2 and $<= 5.1$	Moderate response	Moderate response	No response								
> 5.1	Moderate response	No response	No response								

- Percentage of subjects achieving ACR/EULAR score for remission at each analysis visit If all of the following 4 parameters are fulfilled, it is defined as remission:
 - TJC (68 joints) <= 1
 - o SJC (66 joints) <= 1

 - \circ CRP <= 1 mg/dL
 - \circ SGA \leq 1 cm (on a VAS of 0-100 mm)

Note: All 4 conditions must be fulfilled to be in remission. If any component is a missing value, then ACR/EULAR score for remission will be a missing value.

- Percentage of subjects with a simplified disease activity index (SDAI) score of <= 3.3 at each analysis visit
 - SDAI score is consist of following parameters, and calculated according to below description.
 - o TJC (28 joints)
 - o SJC (28 joints)
 - o SGA (0-10 cm VAS)
 - o PGA (0-10 cm VAS)
 - \circ CRP (mg/dL)

$$SDAI = TJC + SJC + SGA + PGA + CRP$$

Note: If any component is a missing value, then SDAI score will be a missing value.

- Percentage of subjects with a CDAI score of <= 2.8 at each analysis visit
 CDAI score is consist of following parameters, and calculated according to below description.
 - o TJC (28 joints)
 - o SJC (28 joints)
 - o SGA (0-10 cm VAS)
 - o PGA (0-10 cm VAS)

$$CDAI = TJC + SJC + SGA + PGA$$

Note: If any component is a missing value, then CDAI score will be a missing value.

- Percentage of subjects achieving HAQ-DI (<=0.5) at each analysis visit
- Percentage of subjects achieving decrease of baseline HAQ-DI of at least 0.22 at each analysis visit

• Percentage of subjects achieving SF-36v2 of difference >= 5 at each visit

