- If CRP value (mg/dL) is the lower or equal limit of quantitation (i.e. <0.01 mg/dL or =<0.01 mg/dL) then CRP is regarded as 0.01 mg/dL, and used for the calculation of DAS28-CRP, etc. and categorized in <0.01 mg/dL.
- If ESR value (mm/hr) is the upper limit of quantitation (i.e. >=100 mm/hr) then ESR is regarded as 100 mm/hr, and used for the calculation of DAS28-ESR.
- Treatment Sequence Set of preceding study will be used for the analysis by preceding study. This set takes into consideration the initial treatment groups (in RAJ1), a switch from placebo to active treatment at Week 12 (in RAJ3), and a switch from placebo to active treatment at Week 12 or Week 28 (in RAJ4). For subjects in each preceding study, following groups are defined:

Treatment Sequence Set for RAJ1

11 cutiment sequence set for 14 for											
Treatment Sequence	Treatment Sequence	initial treatment									
Code	Label	group									
SEQ J1-1	25mg	ASP015K 25mg									
SEQ J1-2	50mg	ASP015K 50mg									
SEQ J1-3	100mg	ASP015K 100mg									
SEQ J1-4	150mg	ASP015K 150mg									
SEQ J1-5	Placebo	Placebo									

- o 25 mg: subjects who initially treated as ASP015K 25 mg Group
- o 50 mg: subjects who initially treated as ASP015K 50 mg Group
- o 100 mg: subjects who initially treated as ASP015K 100 mg Group
- o 150 mg: subjects who initially treated as ASP015K 150 mg Group
- Placebo: subjects who initially treated as Placebo Group

Treatment Sequence Set for RAJ3

Treatment Sequence	Treatment Sequence	Week 0- Week 12	Week 12- Week 52
Code	Label		
SEQ J3-1	100mg	ASP015K 100 mg	ASP015K 100 mg
SEQ J3-2	150mg	ASP015K 150 mg	ASP015K 150 mg
SEQ J3-3	Placebo to 100mg at Week 12	Placebo	ASP015K 100 mg
SEQ J3-4	Placebo to 150mg at Week 12	Placebo	ASP015K 150 mg
SEQ J3-5	Etanercept	Etanercept	Etanercept

- o 100 mg: subjects who initially treated as ASP015K 100 mg Group
- o 150 mg: subjects who initially treated as ASP015K 150 mg Group
- Placebo to 100 mg at Week 12: subjects who initially treated as Placebo group and switched ASP015K 100 mg at Week 12 and at least one dose of ASP015K 100 mg drug after switched

- Placebo to 150 mg at Week 12: subjects who initially treated as Placebo group and switched ASP015K 150 mg at Week 12 and at least one dose of ASP015K 150 mg drug after switched
- Etanercept: subjects who initially treated as Etanercept Group. Subjects in this group do not shift to this study.

Treatment Sequence Set for RAJ4

Treatment Sequence Set 101 KA104						

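### DAS28-ESR is set to missing at visits where ESR is 0, a small one-directional bias that a substitution rule like those in SAP 7.1 would remove

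*SAP*

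**What the plan says.** SAP 6.1.1 builds DAS28-ESR from the 28-joint tender and swollen counts, ESR and the subject's global assessment (SGA), with ESR entering as 0.70 × ln(ESR). Two rules for gaps follow: "If any component is a missing value, then DAS28-CRP/ESR will be a missing value", and "If ESR is 0 then DAS28-ESR is missing".

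SAP 7.1 treats other limits differently. At or above 100 mm/hr, "then ESR is regarded as 100 mm/hr, and used for the calculation of DAS28-ESR". At or below 0.01 mg/dL, "then CRP is regarded as 0.01 mg/dL, and used for the calculation of DAS28-CRP, etc". No lower substitution for ESR appears anywhere: the section on limits of quantification (SAP 7.11.1) does not mention ESR, and the protocol's own formula (Protocol 5.3.1.5) is silent on zero.

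The results that depend on this score include "Percentage of subjects achieving DAS28-ESR score <2.6 at each analysis visit", "Percentage of subjects achieving DAS28-ESR score <=3.2 at each analysis visit", the EULAR-ESR response categories, and the raw value and change summaries and plots (SAP 6.1.1, 6.1.2, 7.4.1 and Appendix 1). SAP 7.1 also leaves a subject out of change calculations at every visit when the baseline value is missing. For efficacy, that baseline comes from RAJ1, RAJ3 or RAJ4.

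**The concern.** A score that is missing because a component is very good is not missing at random. An ESR of 0 pulls DAS28-ESR down as far as ESR can, and at exactly that point the plan discards the score. The highest ESR readings are kept at 100.

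The remission, low-disease-activity and EULAR-ESR rates then lean low at the affected visits and the mean leans high. Because low CRP is kept and zero ESR is not, the CRP and ESR versions of DAS28 at one visit can rest on different sets of subjects.

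**Working it through.** **Inputs.** The formula, the two cut-points and the missing-data rules come from SAP 6.1.1 and 7.1. The documents do not give the share of readings equal to 0 or any DAS28-ESR remission rate, so those below are assumptions. The plan states no figure to reproduce.

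**What a scored ESR 0 visit would look like.** With ESR set to 1 mm/hr, ln(1) = 0 and the score is 0.56√TJC + 0.28√SJC + 0.014 × SGA. The second and fourth columns show how it moves with other floors: 0.70 × ln(0.5) = −0.485 and 0.70 × ln(2) = +0.485.

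| TJC / SJC / SGA (mm) | Floor 0.5 | Floor 1 | Floor 2 |
|---|---|---|---|
| 2 / 2 / 30 | 1.12 | 1.61 | 2.09 |
| 4 / 4 / 50 | 1.89 | 2.38 | 2.87 |
| 6 / 6 / 50 | 2.27 | 2.76 | 3.24 |
| 9 / 9 / 50 | 2.73 | 3.22 | 3.71 |
| 28 / 28 / 100 | 5.36 | 5.84 | 6.33 |

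At floor 1, the first two rows fall below 2.6, the third below 3.2, the fourth just above 3.2 and the last above 5.1. Most plausible ESR 0 visits would therefore score low, but not all.

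**Effect on a remission rate.** Let p be the share of readings equal to 0, r the remission rate among them, and b the rate among the rest. If missing scores leave the denominator, the plan reports b. The full rate is (1 − p)b + pr, so the understatement is p(r − b). Two assumed pairs span a range:

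| p | r = 95%, b = 30% | r = 80%, b = 60% |
|---|---|---|
| 0.5% | 0.005 × 65 = 0.325 points | 0.005 × 20 = 0.1 points |
| 1% | 0.01 × 65 = 0.65 points | 0.01 × 20 = 0.2 points |
| 3% | 0.03 × 65 = 1.95 points | 0.03 × 20 = 0.6 points |

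The SAP does not state the denominator for DAS28 percentages by visit. If a missing score counted as a failure, the report would show (1 − p)b and the understatement would be pr: from 0.005 × 80 = 0.4 to 0.03 × 95 = 2.85 points.

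**Effect on a mean.** If the ESR 0 visits average D units below the others, the mean is overstated by pD. For scale, 0.70 × ln(5) = 1.127, so an ESR of 5 scores 1.13 above the floor of 1 with the other components equal. With D from 1.0 to 2.5 (assumed), the overstatement runs from 0.005 × 1.0 = 0.005 to 0.03 × 2.5 = 0.075.

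**End of treatment.** SAP 7.11.2 carries components forward, but its instruction names only the CRP version. An observed 0 is not a missing component, so carrying components forward would not restore the score. The general carry-forward sentence in SAP 7.11.4 could be read as putting an earlier score in its place. The text does not settle which applies.

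**The case against.** The best defence is that ESR 0 is a domain problem in a logarithm, not a quantitation limit. DAS28-CRP uses ln(CRP + 1), so it has no such problem. The SAP is also consistent in setting undefined quantities to missing: percent change is missing when baseline is 0 (SAP 7.1), and an ACR component with a zero baseline is dropped (SAP 6.1.1). That stands, so a reader who infers that the SAP contradicts itself goes too far. It is a pre-specified convention that is less good than its neighbours.

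A reader might also infer that the subjects with the least inflammation disappear from every DAS28-ESR result. The documents do not support this. The loss is of one visit's score, except when the zero falls at the preceding-study baseline. An ESR of 0 is the least inflammation by ESR only, and the table shows that the other components can still carry the score above 5.1. The reading itself stays in the raw ESR summaries, and in ACR-ESR it counts as a full reduction from a non-zero baseline. Nor do the documents give any figure to show that the bias grows as treatment lowers ESR.

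The stakes are limited. The protocol's DAS28 remission endpoint uses CRP (Protocol 2.3.2). The treatment-sequence, dose-level and dose-escalation analyses use ACR20-CRP and DAS28-CRP (SAP 7.4.2 to 7.4.4). There is no comparator and no hypothesis test (Protocol 4.1.2; SAP Appendix 1). The bias understates benefit. With 201 subjects from RAJ1, 0.5% is one subject, and the standard error of a 30% rate is √(0.30 × 0.70 / 201) = 3.2 points, more than any exclusion figure above.

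**Conclusion.** The point holds and is minor. Following the plan as written drops DAS28-ESR scores because one component is at its lowest value, and nothing elsewhere in either document restores them. The DAS28-ESR mean, the rates below 2.6 and at or below 3.2, and EULAR-ESR response lean toward worse disease at the affected visits, provided that ESR 0 visits have lower scores on average than the rest, as the formula makes likely. A zero at the preceding-study baseline costs the subject all DAS28-ESR change values and leaves EULAR-ESR improvement undefined.

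The size is probably small: about 0.1 to 2 percentage points in remission if 0.5% to 3% of readings are 0 and missing scores are excluded. That range rests wholly on assumed frequencies and remission rates. DAS28-CRP, SDAI, CDAI and ACR-CRP values are unaffected. The one side effect is that a subject with ESR 0 at baseline has no category in the baseline DAS28-ESR subgroup that SAP 7.8.1 applies to ACR20-CRP.

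**What to change.** Replace the sentence in SAP 6.1.1 with: *If ESR is 0 mm/hr it is regarded as 1 mm/hr for the calculation of DAS28-ESR.* Place it beside the CRP and ESR limit rules in SAP 7.1 and apply it equally to the preceding-study baseline. Report the number of ESR 0 visits. It would help to state, in the same edit, the denominator for DAS28 percentages and how a DAS28-ESR score is obtained at end of treatment.

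The cost is one sentence and one line of code, with a small downside. The floor is a convention: 0.5 or 2 mm/hr would shift the affected scores by 0.49, enough to move some visits across 2.6 or 3.2. It may also differ from how the preceding studies scored ESR 0, which these documents do not show and which should be checked. Because each center measures ESR itself (Protocol 5.3.1.3), the frequency of recorded zeros may vary by site, and a zero may merit a data query before it is scored.

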7 STATISTICAL METHODOLOGY

7.1 General Considerations

- For continuous variables, descriptive statistics will include the number of subjects (n), mean, standard deviation (SD), median, minimum, and maximum.
- For categorical variables: number and percentages of subjects will be described.
- For time-to-event variables: number and percentage of subjects with the event using Kaplan-Meier method, the cumulative event rate will be estimated and a plot will be constructed.
- All data processing, summarization, and analyses will be performed using SAS Drug Development (ver. 4.5), and PC-SAS (ver. 9.4) or higher versions.
- Specifications for table, figures, and data listing formats can be found in the TLF specifications for this study.
- For the definition of subgroups of interest can be referred to Section 7.8.
- Summaries based on FAS and SAF (e.g. disposition, baseline, efficacy data and safety data) will be presented by preceding studies and overall, unless specifically stated otherwise.
- Medical Dictionary for Regulatory Activities (MedDRA) 11.1 will be used as the coding dictionary for adverse event and medical history.
- Confidence interval for binary outcome is continuity corrected in all analysis.
- For the analyses of efficacy and pharmacodynamics variables in this extension study, values at the baseline in the preceding studies (RAJ1, RAJ3, and RAJ4) will be used as the baseline values. However, changes from baseline values of this extension study will also be examined where appropriate. For the analyses of safety, Week 0 of this extension study will be referred to as the baseline; however, changes from baseline values of the preceding studies (RAJ1, RAJ3, and RAJ4) will also be examined where appropriate.
- Change from baseline to post-baseline will be calculated as: post-baseline value baseline value. If the baseline value is missing, then that subject is not included in the calculation at any visit.
- Percent change from baseline to post-baseline will be calculated as: 100 × (change /baseline). If the baseline value is 0 or missing, or post-baseline value is missing, then percent change from baseline to post-baseline is missing.
- The values below the lower limit of quantitation (BQL) for β-D-glucan, hCG, Troponin, CK-MB will be treated as it is and these variables are not used for descriptive statistics

- and displayed in the listings. As for β -D-glucan, it is used for shift-from baseline analysis.

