7.2.2.2 Baseline Disease Activity

[Analysis Set: FAS, SAF, PDAS]

The following baseline disease activity variables will be summarized by descriptive statistics. The summaries will be presented for values at both "Week 0" and "baseline of preceding study".

- o TJC-68
- o TJC-28
- o SJC-66
- o SJC-28
- o SGAP (100 mm VAS)
- SGA (100 mm VAS)
- PGA (100 mm VAS)
- HAQ-DI (scale 0 3)
- o CRP (mg/dL)
- o ESR (mm/hr)
- o DAS28-CRP
- o DAS28-ESR
- o SDAI score
- CDAI score
- WPAI (only for subjects who transferred from studies RAJ3 or RAJ4)
- SF-36V2®

In addition, following baseline efficacy categorical variables will be summarized as well.

- \circ Baseline CRP (< 1.0, >= 1.0)
- Baseline DAS28-CRP/ ESR (<= 3.2, 3.2<-5.1, > 5.1)

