10 APPENDICES

10.1 Appendix 1: Overview of Efficacy Endpoints

Table below summarizes the analyses of the efficacy variables, with "X" indicating that the variable will be analyzed. All analyses will be based on the FAS and presented by preceding studies, unless otherwise specified. No statistical hypothesis testing will be performed.

Overview of Efficacy Endpoints analysis

		Compone	Component for use			r Analysis		
Analysis	Type/Analysis Variable	CRP	ESR	None	RAJ1	RAJ3	RAJ4	Analysis Group
Categori	cal Variables				1	1	1	_
1.1	Percentage of subjects achieving ACR20/50/70 at each visit	X	X		X	X	X	preceding studies
1.2.1	Percentage of subjects achieving ACR20 at each visit Analysis by Treatment Sequence Set of preceding study	X			X			Treatment Sequence Set
1.2.2	Percentage of subjects achieving ACR20 at each visit Analysis by Treatment Sequence Set of preceding study	X				X		Treatment Sequence Set
1.2.3	Percentage of subjects achieving ACR20 at each visit Analysis by Treatment Sequence Set of preceding study	X					X	Treatment Sequence Set
1.3	Percentage of subjects achieving ACR20 at each visit Analysis of Efficacy in Each Dose Level	X			X	X	X	preceding studies

12-Nov-2019 Astellas Page 57 of 94

		Component for use			Study for Analysis			Analysis Croun
Analysis Ty	/pe/Analysis Variable	CRP ESR None		RAJ1	RAJ3	RAJ4	Analysis Group	
1.4.1	Percentage of subjects achieving ACR20 at each interval Influence of Dose Escalation	X			X			Subjects Who Experienced Dose Up to 100 mg
1.4.2	Percentage of subjects achieving ACR20 at each interval Influence of Dose Escalation	X				X		Subjects Who Experienced Dose Up to 150 mg
1.4.3	Percentage of subjects achieving ACR20 at each interval Influence of Dose Escalation	X					X	Subjects Who Experienced Dose Up to 150 mg

12-Nov-2019 Astellas Page 58 of 94

		Component for use			Study fo	r Analysis		
Analysis	Type/Analysis Variable	CRP	ESR	None	RAJ1	RAJ3	RAJ4	Analysis Group

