4	Percentage of subjects achieving "Good Response" or "Moderate Response" using DAS28 EULAR response criterion at each visit	X	X		X	X	X	preceding studies
5	Percentage of subjects in ACR/EULAR remission at each visit	X			X	X	X	preceding studies
6	Percentage of subjects in SDAI <= 3.3 at each visit	X			X	X	X	preceding studies

12-Nov-2019 Astellas Page 60 of 94

Anglewin Toma/Anglewin Wasinkla			ent for use		Study fo	r Analysis		A salada Gara
Analysis T	ype/Analysis Variable	CRP	ESR	None	RAJ1	RAJ3	RAJ4	Analysis Group
7	Percentage of subjects in CDAI <= 2.8 at each visit			X	X	X	X	preceding studies
8.1	Percentage of subjects achieving HAQ-DI (<=0.5) at each visit			X	X	X	X	preceding studies
8.2	Percentage of subjects achieving decrease of baseline HAQ-DI in preceding study of at least 0.22 at each visit			X	X	X	X	preceding studies
9	Percentage of subjects achieving SF-36v2 of difference >= 5 at each visit			X	X	X	X	preceding studies
Continuou	s Variables	•				•		
10.1.1	Raw value and change from baseline of preceding study in DAS28 score at each visit	X	Х		X	Х	X	preceding studies
10.1.2	Raw value and change from Week 0 in DAS28 score at each visit	X			X	X	X	preceding studies
10.2.1	Raw value and change from baseline of preceding study in DAS28 score at each visit Analysis by Treatment Sequence Set of preceding study	Х			X			Treatment Sequence Set
10.2.2	Raw value and change from baseline of preceding study in DAS28 score at each visit Analysis by Treatment Sequence Set of preceding study	Х				Х		Treatment Sequence Set

12-Nov-2019 Astellas Page 61 of 94

		Compon	ent for use		Study fo	r Analysis		
Analysis T	Sype/Analysis Variable	CRP	ESR	None	RAJ1	RAJ3	RAJ4	Analysis Group
10.2.3	Raw value and change from baseline of preceding study in DAS28 score at each visit Analysis by Treatment Sequence Set of preceding study	X					X	Treatment Sequence Set
10.3	Raw value and change from baseline of preceding study in DAS28 score at each visit Analysis of Efficacy in Each Dose Level	X			Х	X	X	preceding studies
10.4.1	Raw value and change from baseline of preceding study in DAS28 score at each interval Influence of Dose Escalation	X			Х			Subjects Who Experienced Dose Up to 100 mg
10.4.2	Raw value and change from baseline of preceding study in DAS28 score at each interval Influence of Dose Escalation	X				Х		Subjects Who Experienced Dose Up to 150 mg

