The patient must have a score for >= 6 of the 8 categories. If there are less than 6 categories completed, a HAQ-DI cannot be computed, whether the missing categories are due to missing values or they do not apply to the respondent. Individual questions within a category are not imputed. Therefore the maximum score in each category is based on non-missing questions, and a category score is missing when all questions within a category are missing.

There are three steps to compute the HAQ-DI score.

- 1. For each category, compute the category score by using the highest question score.
- For example, in the category "Eating" there are 3 questions, a subject responds with a 1, 2, and 0, respectively.

Category	Question	Subject Reported Response
Eating	1) Cut your own meat	1
	Lift a full cup or glass to your mouth	2
	3) Open a new milk carton	0

- The highest score is 2, so the category score is 2 for this subject.
- 2. Adjust for use of "aids or devices" and/or "help from another person" when indicated in the checkbox(es)
 - If the category score is < 2 but at least one "aids or devices" or "help from another person" box is checked, the category score is set equal to 2.
 - If the category score is < 2 and none of the "aids or devices" or "help from another person" boxes is checked, the category score remains.
 - If the category score is 2, it remains 2, and if a three, it remains a three.
- 3. Divide the summed category scores by the number of categories answered (must be a minimum of 6) to obtain a HAQ-DI score of 0-3, with higher scores indicating greater disability (3 = worst functioning).

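### The HAQ-DI improvement rate (fall of at least 0.22; SAP 6.1.1 and Appendix 1 item 8.2) counts as failures subjects whose parent-study baseline is too low for that fall to be possible

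*SAP*

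**What the plan says.** SAP 6.1.1 lists two HAQ-DI percentages: "Percentage of subjects achieving HAQ-DI (<=0.5) at each analysis visit" and "Percentage of subjects achieving decrease of baseline HAQ-DI of at least 0.22 at each analysis visit". Neither carries a condition on the starting score. Appendix 1 item 8.2 names the reference point for the second: "Percentage of subjects achieving decrease of baseline HAQ-DI in preceding study of at least 0.22 at each visit". That agrees with SAP 7.1, under which, for efficacy, "values at the baseline in the preceding studies (RAJ1, RAJ3, and RAJ4) will be used as the baseline values".

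On the population, Appendix 1 states: "All analyses will be based on the FAS and presented by preceding studies, unless otherwise specified". The FAS (SAP 5.1) requires one dose and any efficacy measurement. The extension's eligibility criteria (Protocol 3.2 and 3.3) set no minimum HAQ-DI.

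A baseline that leaves no room to improve is handled only for ACR response. The rule that begins "If the baseline value is 0 in some of ACR components, then that" goes on to take such a component out of the calculation. For change scores, SAP 7.1 removes a subject only when the baseline is missing.

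SAP 7.2.2.2 summarises HAQ-DI by descriptive statistics at both parent baseline and Week 0. It then adds: "In addition, following baseline efficacy categorical variables will be summarized as well". That list covers CRP and DAS28 only.

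**The concern.** Part of the denominator of item 8.2 can never register a success. In the table these subjects look the same as subjects who could have improved and did not. Their share depends on who entered each parent study, not on the response to ASP015K. The results are laid out by RAJ1, RAJ3 and RAJ4. These are not randomised groups, so nothing makes the share equal across columns.

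A reader cannot undo this from the planned output:

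- A mean, SD, median and range do not give the share of subjects below a cut.
- The HAQ-DI visit windows (SAP 7.11.5) start at extension Week 0, which follows RAJ1 Week 16 or RAJ3/RAJ4 Week 52. Their rows do not show status before parent-study treatment.
- SAP 7.4.2 adds parent-study visits only for ACR20-CRP and DAS28-CRP.

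The SAP does better on neighbouring endpoints. It drops a zero-baseline component from ACR, and it tabulates baseline DAS28 at 3.2, the same cut as its DAS28 ≤3.2 endpoint. Protocol 2.3.2 lists only change from baseline for HAQ-DI. The percentages are SAP additions, so the SAP is the place to make them readable.

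**Working it through.** The plan states no figure for this endpoint, so there is none to reproduce. The check uses the scoring rule and then a range for the unknown share.

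**1. Attainable scores.** SAP Appendix 4 scores each category 0, 1, 2 or 3 and instructs: "Divide the summed category scores by the number of categories answered (must be a minimum of 6) to obtain a HAQ-DI score of 0-3". The score is therefore S/k, with S a whole number and k = 6, 7 or 8.

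| Categories answered (k) | Scores below 0.22 | Lowest score from which a fall of 0.22 is possible |
|---|---|---|
| 8 | 0; 1/8 = 0.125 | 2/8 = 0.25 |
| 7 | 0; 1/7 = 0.143 | 2/7 = 0.286 |
| 6 | 0; 1/6 = 0.167 | 2/6 = 0.333 |

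**2. Largest possible fall.** The minimum score is 0, so the largest fall from a baseline B is B itself. For B < 0.22 the largest fall is 0.167, which is less than 0.22. Such a subject is a non-responder at every visit with a HAQ-DI score, however many categories are answered at that visit.

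**3. Effect on the reported rate.** Let q be the share with parent baseline below 0.22, and r the response rate among the others. The all-FAS rate is

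0 × q + r × (1 − q) = r(1 − q).

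Its ceiling is 1 − q.

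**4. Size.** Neither q nor r is in the documents. For illustration, take r = 65%:

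| q (assumed) | Reported rate = 0.65 × (1 − q) | Ceiling |
|---|---|---|
| 2% | 0.65 × 0.98 = 63.7% | 98% |
| 5% | 0.65 × 0.95 = 61.75%, about 62% | 95% |
| 10% | 0.65 × 0.90 = 58.5% | 90% |
| 20% | 0.65 × 0.80 = 52.0% | 80% |

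The relative shortfall is q itself, whatever r is. Two columns with the same r but q of 5% and 20% would differ by 61.75 − 52.0 = 9.75 points. Restricting the denominator to parent baseline ≥0.22 returns r = 65% in every row.

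**The case against.** The strongest reply is that nothing is tested. Appendix 1 plans no hypothesis tests, the study has no comparator, and SAP 7.4 sets up no contrast between preceding studies. The columns also differ in starting dose (50 mg/day from RAJ1, 100 mg/day from RAJ3 and RAJ4) and in background DMARD rules. A difference between them could not be put down to ASP015K even with a restricted denominator. The all-FAS rate is a true description of how many treated subjects improved by that amount. Raw HAQ-DI and change from parent baseline are reported at each visit (Appendix 1 item 13) and depend on no cut. The baseline minimum will show whether very low scores occur at all. Finally, the parent-study entry criteria are not in these documents and RAJ1 enrolled moderate to severe RA (Protocol 1.2.4), so q could be close to zero.

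All of this stands, and it sets the severity. It does not answer the floor: a minimum shows that low scores exist, not how many, and the rate still mixes inability to respond with failure to respond.

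A reader might infer three stronger claims that the documents do not support.

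- **The HAQ-DI ≤0.5 percentage is biased upward because some subjects already meet it at parent baseline.** It is a state measure, like DAS28 <2.6, SDAI ≤3.3 and CDAI ≤2.8 in the same section. A subject already there can worsen out of it, and staying there is a valid long-term outcome. Conditioning on baseline above 0.5 would be a preference, not a correction.
- **Regional comparisons are distorted.** SAP 7.8.2 names HAQ-DI without saying which summary. Appendix 1 has regional rows for ACR and DAS28 but none for items 8.1 or 8.2.
- **The zero-baseline ACR rule shows that the SAP expects HAQ-DI scores of 0.** The rule covers all ACR components, where percent change cannot be computed from 0. It says nothing about how often HAQ-DI is 0.

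**Conclusion.** The point holds for item 8.2 only. That subjects with a parent baseline below 0.22 are fixed non-responders follows from the scoring rule and needs no assumption. The size does need assumptions: 62% to 52% rests on r = 65% and q of 5% to 20%, neither of which the documents give. The 10-point gap needs two columns at opposite ends of that range, so it is not an estimate of bias in this study. This is a cheap improvement of low severity, on a descriptive endpoint that changes no inference.

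**What to change.** 1. In SAP 6.1.1 and Appendix 1 item 8.2, report the fall of at least 0.22 among FAS subjects with parent baseline HAQ-DI ≥0.22. Keep the all-FAS rate as a second row.
2. In SAP 7.2.2.2, add the number and percentage with parent baseline HAQ-DI <0.22, by preceding study. Add the same for ≤0.5, as context for item 8.1.
3. Leave item 8.1 on the FAS.

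The cost is SAP wording, one denominator flag, one extra row in the item 8.2 table, two baseline counts, and a slightly smaller denominator in the restricted row. No new data are needed, because parent-baseline HAQ-DI is already to be summarised. If the SAP is not reopened, SAP section 1 provides for changes to the planned analyses to be justified in the study report.
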